5.2 Exclusion Criteria

Participants are excluded from the study if any of the following criteria apply:

Medical Conditions

1. Clinically significant (i.e., active) uncontrolled intercurrent illness including, but not limited to:
 - Active infection (i.e., requiring systemic antibiotics or antifungals)
 - Uncontrolled arterial hypertension (i.e., systolic blood pressure > 150 mmHg, diastolic blood pressure > 100 mmHg)
 - Symptomatic congestive heart failure (\geq New York Heart Association Classification Class II), unstable angina, myocardial infarction or a coronary revascularization procedure within 180 days of study entry
 - Calculated average QT interval corrected using Fridericia's formula (QTcF) of > 450 msec for males and > 470 msec for females.
 - A history of additional risk factors for Torsades de Pointes (e.g., clinically relevant hypokalemia, family history of Long QT Syndrome)

- The use of concomitant medications that prolong the QT/QTc interval
- Severe cardiac arrhythmia requiring medication
- Cerebral vascular accident/stroke
- Clinically significant liver disease consistent with Child Pugh Class B or C; and/or
- Any psychiatric illness/social situations that would limit compliance with study requirements.

2. Presence of brain metastases unless clinically stable (without evidence of progression by imaging for at least four weeks prior to the first dose of study intervention and any neurologic symptoms have returned to baseline), no evidence of new brain metastases, and on a stable or decreasing dose or without steroids for at least 14 days prior to study intervention. Participants with carcinomatous meningitis are excluded regardless of clinical stability. Central nervous system imaging at Screening is not mandatory.
3. Has a known additional malignancy that is progressing and/or requires active treatment. In addition, participants are excluded who were diagnosed with another malignancy within 3 years of starting study intervention. Exceptions include fully resected basal cell carcinoma of the skin or squamous cell carcinoma of the skin, *in situ* cervical cancer, fully resected ductal carcinoma *in situ*, and Stage IA noninvasive grade I endometrioid endometrial cancer, that has undergone curative therapy. Participants with other localized malignancies treated with curative intent need to be discussed with the Medical Monitor. Participant must not have any known history of myelodysplastic syndrome or acute myeloid leukemia.
4. Has known ataxia telangiectasia
5. Participants with tumors harboring previously identified ATM mutations
6. Individuals with known human immunodeficiency virus and/or active viral hepatitis (B and/or C), and individuals on viral hepatitis B therapy are excluded. However, individual with Hepatitis C treated with curative therapy are not considered actively infected.
7. Has a history or current evidence of any condition, therapy, and/or laboratory abnormality that might confound the results of the trial, interfere with the participant's participation for the full duration of the trial, and/or is not in the best interest of the participant to participate, in the opinion of the treating investigator.

Gastrointestinal Conditions

8. Serious gastrointestinal bleeding within 3 months, refractory nausea and vomiting, uncontrolled diarrhea, known malabsorption, significant small bowel resection or gastric bypass surgery, use of feeding tubes, other chronic gastrointestinal disease (including exocrine pancreatic insufficiency requiring pancreatic enzyme replacement therapy) and/or other situation that may preclude adequate absorption of oral medications

Prior/Concomitant Therapy

9. Participants who may have received any of the following anticancer therapy(ies), or concomitant medications within the following windows per the first day of study intervention administration:

- Hematopoietic growth factors (including erythropoietin, darbepoetin, granulocyte-colony stimulating factor, granulocyte macrophage-colony stimulating factor, and platelet stimulators [e.g. eltrombopag, romiplostim, or IL-11]) and blood transfusions within 2 weeks.
- Anticancer treatment within 28 days or 5 half-lives, whichever is shorter, except for nitrosoureas or mitomycin C (within 6 weeks).
- Participants receiving prior treatment with an ATM inhibitor.
- Prior curative-intent radiotherapy within 4 weeks. Prior palliative radiotherapy to metastatic lesion(s) is permitted provided it was completed \geq 2 weeks prior to study enrollment and toxicities have recovered to Grade \leq 1.
- Major surgery within 4 weeks and not recovered for side effects Grade \leq 1, according to investigator's judgment.
- Any other type of anticancer therapy, not listed above, within 4 weeks.
- Clinical substrates of CYP3A4 with narrow therapeutic index. Stop at least 1 week before study intervention until safety follow-up visit.
- Strong inhibitors or inducers of CYP3A4 or P-gp that cannot be discontinued as outlined in Section 6.5.3. Examples of strong inhibitors of CYP3A4 and P-gp inhibitors or strong inducers of CYP3A are provided in [Table 9](#).
- Additional excluded concomitant medications include irinotecan, oral direct thrombin inhibitors, and digoxin. Stop at least 1 week before study intervention until safety follow-up visit.
- Concomitant treatment with proton pump inhibitors is prohibited. The administration of H₂-receptor antagonists will be permitted as long as they are not administered for 12 hours before or 2 hours after the dosing of M4076. Antacids cannot be administered 2 hours before or 2 hours after the dosing of M4076.

10. Participants not recovered from AEs (i.e., Grade \leq 1) of prior anticancer therapies. Exception: Grade 2 AEs not constituting a safety risk, based on the Investigator's judgement, must be consulted with the Sponsor prior to enrolment.

Prior/Concurrent Clinical Study Experience

- 11. Is currently participating and receiving study therapy or has participated in a study of an investigational agent and received study therapy and/or used an investigational device within 4 weeks of the first M4076 administration of study intervention or longer if described elsewhere.
- 12. Hypersensitivity to the active substance or to any of the excipients of M4076.

Other Exclusions

- 13. Pregnant or breastfeeding.
- 14. Part 1B only (food effect cohort): participants unable to consume a low-fat meal as specified in [Appendix 8](#).

5.3 Lifestyle Considerations

No specific lifestyle or dietary restrictions are required throughout the study. Tobacco use status, e.g., former, current or never, will be collected at screening and recorded in the eCRF.

Refer to [Appendix 8](#) for timing of meals in Parts 1A and 1B.

5.4 Screen Failures

Individuals who do not meet the criteria for participation in this study (screen failure) may be rescreened once after the reason for screening failure has been addressed. Rescreened participants will be reconsented and assigned a new participant number and will undergo Screening procedures as planned by the protocol. Any previous screening tests can be used for rescreening, provided they are within the new screening window.

6 Study Intervention(s)

Study intervention is any investigational intervention(s), marketed product(s), placebo, or medical device(s) intended to be administered to a study participant per the study protocol. Study intervention is used instead of “study drug, Investigational Medicinal Product, or study treatment”.

6.1 Study Intervention Administration

Participants are planned to continue with study intervention (see [Table 8](#)) until documented disease progression, discontinuation due to adverse events, death or withdrawal from the study, whichever occurs earlier.

Fasting Window Definition

For Part 1A - The fasting window is defined as: 2 hours pre-dose to 1-hour post-dose in general, and 2 hours pre-dose to 4 hours post-dose on days where PK-time matched triplicate ECG will be collected. This fasting strategy facilitates more frequent daily dosing regimens and alleviates potential discomfort for advanced cancer patients during the dose escalation phase.

For Part 1B - The fasting window is defined as: 10 hours pre-dose to 4 hours post-dose.

Table 8 Study Intervention Details

Intervention Name	M4076
Type	Drug
Dose Formulation	Film-coated tablets
Unit Dose Strengths	50 mg
Dose Amount	M4076 will be administered orally, as planned, once daily per the dose escalation schema (Figure 2) and as determined by the SMC based on safety, tolerability, and preliminary PK and, if appropriate, Pd data. MTD/RDE to be determined. See Sections 4.1.1 and 6.6 for more information.

Frequency	Once daily; schedules may be adapted
Route of Administration	Oral
Use	Experimental
IMP/NIMP	IMP
Sourcing	Provided centrally by the Sponsor.
Packaging and Labeling	Study Intervention will be provided in participant kits containing M4076 tablets in blisters. Each kit will be labeled per country requirement.

IMP = investigational medicinal product; MTD = maximum tolerated dose; NIMP = non investigational medicinal product; Pd = pharmacodynamics; PK = pharmacokinetic; RDE = recommended dose for evaluation; SMC = safety monitoring committee.

6.2 Study Intervention(s) Preparation, Handling, Storage, and Accountability

The Investigator, institution, or the head of the medical institution (where applicable) is responsible for study intervention accountability, reconciliation, and record maintenance (i.e., receipt, reconciliation, and final disposition records).

- Upon receipt of the study intervention(s), the Investigator or designee will confirm appropriate temperature conditions have been maintained during transit and any discrepancies are reported and resolved before use. Also, the responsible person will check for accurate delivery. Further guidance and information for study intervention accountability are provided in the Pharmacy Manual.
- Only participants enrolled in the study may receive study intervention(s) and only authorized site staff may supply it. All study intervention(s) will be stored in a secure, environmentally controlled, and monitored (manual or automated) area, per the labeled storage conditions, and with access limited to the Investigator and authorized site staff.
- Dispensing will be recorded on the appropriate accountability forms so that accurate records will be available for verification at each monitoring visit.
- Study intervention(s) accountability records at the study site will include the following:
 - Confirmation of receipt, in good condition and in the defined temperature range.
 - The inventory provided for the clinical study and prepared at the site.
 - The dose(s) each participant used during the study.
 - The disposition (including return, if applicable) of any unused study intervention(s).
 - Dates, quantities, batch numbers, medication numbers, expiry dates, and the participant numbers.
- The Investigator site will maintain records, which adequately documents that participants were provided the doses specified in this protocol, and all study intervention(s) provided were fully reconciled.
- Unused study intervention(s) will not be discarded or used for any purpose other than the present study. No study intervention that is dispensed to a participant may be re-dispensed to a different participant.

- A Study Monitor will periodically collect the study intervention(s) accountability forms.
- Further guidance and information for the final disposition of unused study intervention(s) are provided in the Pharmacy Manual.

6.3 Measures to Minimize Bias: Study Intervention Assignment and Blinding

6.3.1 Study Intervention Assignment

The IXRS will be used to assign unique participant numbers, allocate participants to study intervention group at the randomization visit, and study intervention to participants at each study intervention visit.

Before the study is initiated, the directions for the IXRS will be provided to each site. The site will contact the IXRS prior to starting study intervention administration for each participant.

For Part 1B, after confirmation of participant's eligibility prior to study intervention administration, participants will be centrally allocated to either (1) fasted followed by fed, or (2) fed followed by fasted in a 1:1 ratio using an IXRS and per a computer-generated randomization list.

6.3.2 Blinding

This is an open-label study. Participants and Investigators will be aware of study intervention assignments.

Reduction of bias is mitigated by the randomized design in Part 1B (preliminary food effect assessment), which will use an IXRS to assist in randomization to fed/fasting schedules. The IXRS will also be used for study intervention assignment.

6.4 Study Intervention Compliance

When participants are dosed at the site, they will receive study intervention directly from the Investigator or designee, under medical supervision. The date and time of each dose administered in the clinic will be recorded in the source documents and recorded in the CRF. The dose of study intervention and study participant identification will be confirmed at the time of dosing by a member of the study site staff other than the person administering the study intervention.

When participants self-administer study intervention(s) at home, compliance with study intervention will be assessed at each visit. Compliance will be assessed by direct questioning, counting returned tablets during the site visits and documented in the source documents and CRF. Any deviation(s) from the prescribed dosage regimen are recorded in the CRF.

A record of the number of tablets dispensed to and taken by each participant will be maintained and reconciled with study intervention and compliance records. Intervention start and stop dates, including dates for intervention delays and/or dose reductions will also be recorded in the CRF.

6.5 Concomitant Therapy

Record in the CRF all concomitant therapies (e.g., medicines or nondrug interventions) used from the time the participant signs the informed consent until completion of the study, including any changes. For prescription and over-the-counter medicines, vaccines, vitamins, and herbal supplements, record the name, reason for use, dates administered, and dosing information.

Contact the Medical Monitor for any questions on concomitant or prior therapy.

6.5.1 Rescue Medicine

There is no specific treatment or medicine available to counteract the inhibition of ATM intended by M4076. For any unwanted events during study intervention with M4076, the oncological standards in supportive care should be applied.

6.5.2 Permitted Medicines

Any medicines that are considered necessary to protect the participant's welfare in emergencies may be given at the Investigator's discretion, regardless if it results in a protocol deviation.

Outside the DLT observation period in Part 1A of the study, prophylactic or therapeutic use of hematopoietic growth factors is permitted to prevent toxicities requiring study intervention interruption or discontinuation. During the DLT observation period, prophylactic use is prohibited. Therapeutic use, if deemed necessary by the Investigator, is allowed and may constitute a DLT (see Section 6.6.2 for details of DLT criteria).

The administration of H₂-receptor antagonists is permitted as long as they are not administered for 12 hours before or 2 hours after the dosing of M4076. Antacids cannot be administered 2 hours before or 2 hours after the dosing of M4076.

The continuation of hormone therapy is allowed throughout the study if the participant has been on stable treatment for the last 3 months prior to enrollment and the Investigator recommends the need to continue this during the study.

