6.6.2 Dose-limiting Toxicities – Definition and Criteria

A DLT is defined as any of the following AEs according to the National Cancer Institute Common Terminology Criteria for Adverse Events (NCI-CTCAE) Version 5.0 assessed by the Investigator and/or the Sponsor at any dose, judged not to be related to the underlying disease or any previous or concomitant medication or concurrent condition, occurring during the DLT observation period, which for Part 1A starts on the first day of study intervention (Day 1) and has a duration of 21 days.

Study accrual will be halted, pending discussions with the SMC or the study Sponsor, if there is an occurrence of a Grade 5 toxicity by the NCI-CTCAE Version 5.0 attributable to the treatment regimen or if more than 1 DLT is seen in DL 1 in Part 1A.

The treatment of toxicities with transfusions or growth factors (e.g., granulocyte-colony stimulating factor, erythropoietin) is not permitted during the DLT period and if it occurs will be considered a DLT.

AEs judged as DLT will include:

- Any Grade ≥ 3 non-hematologic AE with exception of:
 - Single laboratory values out of normal range that have no clinical correlate and resolve to Grade ≤ 1 or to baseline within 7 days with adequate medical management or asymptomatic Grade 3 lipase or amylase elevation (> 5 ULN) not associated with clinical manifestation of pancreatitis.
 - Infusion-related reaction resolving within 6 hours from the end of infusion and controlled with medical management (for iv compounds only)
 - Diarrhea persisting < 72 hours after initiation of medical management
 - Nausea and vomiting of ≤ 72 h duration with adequate and optimal therapy
 - Transient (≤ 72 h) fatigue, local reactions, flu-like symptoms, fever, headache, hypertension that resolves to Grade ≤ 1 with adequate treatment
 - Grade 3 non-recurrent skin toxicity that resolves to Grade ≤ 1 in less than 7 days after initiation of medical management
 - Tumor flare phenomenon defined as local pain, irritation, or rash localized at sites of known or suspected tumor that resolve to Grade ≤ 2 within 6 days
 - Any death clearly due to the underlying disease or extraneous causes

- Grade ≥ 3 neutropenia with clinical signs/symptoms, such as fever $> 38.5^{\circ}\text{C}$ (e.g., for febrile neutropenia, an ANC $< 1000/\text{mm}^3$ with single temp of 38.3°C [101°F] or a sustained temperature of $\geq 38^{\circ}\text{C}$ [100.4°F] for more than one hour)

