- Grade ≥ 3 thrombocytopenia with medically concerning bleeding
- Any Grade ≥ 4 hematologic AE, except:
 - Isolated Grade 4 lymphopenia without clinical correlate
 - Any Grade 4 neutropenia of < 7 days' duration not associated with any clinical symptoms
- All events of ALT $\geq 3 \times$ upper limit of normal (ULN) and bilirubin $\geq 2 \times$ ULN ($> 35\%$ direct bilirubin) or ALT $> 3 \times$ ULN and international normalized ratio (INR) > 1.5 , if INR measured, may indicate potential severe liver injury (possible Hy's Law), will require prompt permanent discontinuation from the study, and will be reported as an SAE (excluding studies of hepatic impairment or cirrhosis):
 - Without initial findings of cholestasis (elevated serum ALP).
 - In the absence of other reasons than drug toxicity to explain the laboratory constellation (e.g., viral hepatitis A, B, C or co-medication).
 - In the absence of other reasons than drug toxicity to explain the laboratory constellation.
- Any AE leading to the inability to deliver at least 80% of the planned total dose for the DLT period, except in situations other than toxicity, e.g. participant noncompliance or logistical issues with study intervention delivery.
- Death not clearly attributed to underlying disease or alternative cause.
- Additionally, the SMC may identify as a DLT:
 - A TEAE (inside or outside of the DLT period) that in the opinion of the SMC is of potential clinical significance such that further dose escalation would expose participants to unacceptable risk

The SMC must confirm any DLT.

If any change is made to the grade or causality of an AE during the study that may alter its DLT status, the Sponsor must be informed immediately as this may affect dose escalation decisions.

Additionally, participants excluded from the DLT analysis set may be replaced; the decision will be made by the SMC.

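### Protocol Sections 6.5.2 and 6.6.2 give opposite rules on whether therapeutic growth factors are permitted in the 21-day DLT period, and differ on whether their use is a DLT

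*Protocol*

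**What the plan says.** Protocol Section 6.5.2 first deals with the time outside the DLT observation period, where "prophylactic or therapeutic use of hematopoietic growth factors is permitted to prevent toxicities" that would lead to interruption or discontinuation. For the DLT period itself it bans prophylactic use and then says: "Therapeutic use, if deemed necessary by the Investigator, is allowed and may constitute a DLT". It refers the reader to Section 6.6.2 for the DLT criteria. Its growth-factor rule does not mention transfusions.

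Protocol Section 6.6.2 covers both transfusions and growth factors given to treat toxicities. It says that such treatment "is not permitted during the DLT period and if it occurs will be considered a DLT". This sentence stands before the list of adverse events judged as DLTs. That list does not include growth-factor use, and it exempts Grade 4 neutropenia of under 7 days' "duration not associated with any clinical symptoms". The section ends the matter procedurally: "The SMC must confirm any DLT". It also halts accrual, pending discussion, "if more than 1 DLT is seen in DL 1 in Part 1A".

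**The concern.** A site treating a participant with a cytopenia in the first 21 days finds one section that leaves growth factors to the Investigator's judgement and another that forbids them. It also finds one section that makes DLT status conditional and another that makes it automatic.

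Two things are at stake. The first is conduct: whether the use is a permitted treatment or a breach, with what follows for dosing and for deviation reporting. The second is the data: DLT occurrence is among the primary endpoints (Protocol Section 3), and the number of DLTs per dose level, with the number of evaluable participants, is what updates the Bayesian dose-toxicity model (Protocol Appendix 12).

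**Working it through.** The plan gives no figure to reproduce here, so the check is a comparison of text followed by simple proportions.

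**Step 1. The two rules side by side, within the DLT period.**

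| Question | Section 6.5.2 | Section 6.6.2 |
|---|---|---|
| Therapeutic growth factor: permitted? | Yes, if the Investigator judges it necessary | No |
| Therapeutic growth factor: a DLT? | It may be; see 6.6.2 | It will be |
| Transfusion: permitted? | Silent | No |
| Transfusion: a DLT? | Silent | It will be |

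The conflict is confined to the two growth-factor rows.

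**Step 2. What turns on permission.** Three rules attach to a drug that is not permitted:
- Protocol Section 6.5.3: if such a drug becomes necessary, study intervention must be interrupted and permanent discontinuation discussed with the medical monitor.
- Protocol Section 7.1: use of such a drug is listed among the reasons for withdrawal from study intervention.
- SAP Section 10.2.1: receipt of a prohibited concomitant medication is an important protocol deviation.

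Under 6.5.2 none of these follows from therapeutic growth-factor use. Under 6.6.2 all three can. An interruption also bears on the 80% dosing threshold in the DLT criteria and the DLT analysis set. With 21 daily doses, 80% is 0.80 × 21 = 16.8 doses, so five missed doses leave 16/21 = 76.2%, below the threshold.

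**Step 3. What turns on *may* against *will*.** Take a participant with asymptomatic Grade 4 neutropenia of under 7 days who is given a growth factor therapeutically.
- On the 6.6.2 list of adverse events: exempt, so not a DLT by that route.
- On the 6.6.2 sentence about growth factors: a DLT.
- On 6.5.2: it depends on the 6.6.2 criteria. If these are read as the list, the answer is no; if they include the separate sentence, it is yes.

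**Step 4. Is it settled elsewhere?** The DLT analysis set (Protocol Section 9.3, SAP Section 8.1), the intercurrent-event strategies (Protocol Section 3, SAP Section 5) and the DLT analysis (SAP Section 15.1) contain no growth-factor rule. SAP Section 15.1 takes DLT status from the SMC's decision.

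**Step 5. Size of one reclassification.** These are raw proportions on assumed counts, not model output:
- Cohort of 3: 0/3 = 0% becomes 1/3 = 33.3%.
- Six participants at a dose: 1/6 = 16.7% becomes 2/6 = 33.3%.
- Target DLT probability for the MTD: 30%.
- First dose level: a count of 1 that becomes 2 meets the accrual-halt condition.

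**The case against.** The best defence is that 6.5.2 sets no rival DLT rule. It says *may* and sends the reader to 6.6.2, which says *will*, so on a natural reading 6.6.2 governs DLT status. This has force and makes the *may*/*will* difference the weaker limb. It does not close the matter, because 6.6.2 holds both a list that omits growth-factor use and a sentence that makes it decisive. Nor can a pointer to DLT criteria settle permission, which 6.5.2 grants in its own words.

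Second, the SMC confirms every DLT, and both dose-toxicity models in SAP Section 15.1 use its decisions. A reader might infer that disagreement between sites feeds straight into the model. The documents do not support that: one body makes the classification that counts, and the SAP tabulates Investigator and SMC calls separately. But naming who decides does not say which text to apply.

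Third, 6.5.2 lets necessary medicines be given in emergencies even if a deviation results. That covers part of the ground, but it treats the use as a possible deviation and does not say whether ordinary therapeutic use is one.

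Four stronger readings are tempting and should not be drawn:
- *Transfusions are caught in the same contradiction.* They are not; only 6.6.2 addresses their use in the DLT period.
- *Growth-factor use alone fixes the outcome in the Step 3 case.* Other routes to a DLT remain, such as an adverse event preventing 80% dosing or designation by the SMC.
- *This is the likeliest DLT question in the trial.* Cytopenia is the only adverse event of special interest, but on nonclinical grounds. No document gives a rate of Grade 4 neutropenia or of growth-factor use, and the risks added from this study's own data are rash and hypersensitivity.
- *The next-dose recommendation would change.* The prior is redacted, the model borrows across doses, and its recommendation does not bind the SMC. A stand-in prior at a single dose would not show what the trial's model does.

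**Conclusion.** The protocol is wrong as written for therapeutic growth factors in the DLT period. The conflict on permission is plain, and nothing in the protocol or SAP resolves it. The conflict on DLT status is real but softer. The point deserves correction because it touches a primary endpoint, the counts that update the model and the accrual halt at the first dose level.

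Its size is one participant at a time: 0/3 to 1/3 in a usual cohort. That shift would follow from any reclassified DLT, so it shows sensitivity and says nothing about how often this case arises.

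The conclusion rests on two assumptions. One is that the ban in 6.6.2 makes a growth factor a nonpermitted drug for Sections 6.5.3 and 7.1 and a prohibited medication for SAP Section 10.2.1; Section 6.5.3 does not itself name growth factors as prohibited during treatment. The other is that no overriding convention exists in the SMC charter, which is not among the documents read. Such a convention would guide the SMC but would leave the protocol's two instructions to sites unreconciled.

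**What to change.** Replace the two passages with one statement, used in both 6.5.2 and 6.6.2, on (a) whether therapeutic growth factors are permitted in the DLT period and (b) whether their use is a DLT automatically or conditionally, and if conditionally, on what. Make clear how it relates to the 6.6.2 list, including the neutropenia exemption. Align it with 6.5.3 and 7.1, so that it is clear whether interruption, withdrawal and deviation reporting follow. This review takes no position on which rule is right; that choice belongs to the sponsor and the SMC.

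Then check any DLT classification already made that involved growth-factor use, so that one rule applies across cohorts. The documents do not show that any such case exists, so the check may find nothing. The cost is a short protocol amendment and a limited record check.
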